6.3 Primary Outcome

The primary outcome, the difference between the VAS symptom scores for atorvastatin and placebo, will be estimated as the predictive overall margin of a linear regression model with the difference (atorvastatin minus placebo) as the dependent variable and the stratification factors in the randomization (i.e. centre and previous statin discontinuation) as covariates. The estimate and its 95% confidence interval will be presented, with a P-value for the null hypothesis that the difference is zero.

The primary analysis will be performed on the full analysis set. A secondary analysis will be performed on the per protocol set.

6.4 Secondary Outcomes

All secondary outcomes will be analysed on the FAS, except where noted otherwise.

6.4.1 Dichotomous SAMS classification

The proportion of patients with confirmed SAMS will be estimated as the number of patients with confirmed SAMS divided by the total number of patients in the full analysis set. A 95% confidence interval for the proportion will be estimated with the Wilson score confidence interval²⁰.

6.4.2 Relationship between muscle symptom intensity and atorvastatin and metabolites level in blood

The correlations between differences in muscular symptom intensity and levels of atorvastatin and metabolites among patients with confirmed SAMS will be estimated with Spearman rank correlation coefficients, with 95% confidence intervals estimated by the Bonett-Wright approximation²¹. In addition, scatter plots and linear regression analyses may be used to illustrate the associations.

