1.1 Background and rationale

Statin non-adherence (i.e. patients not taking their prescribed drugs) remains a major public health concern in cardiovascular disease patients, leading to adverse outcomes in terms of morbidity, mortality and healthcare costs¹⁻³. The principal reason for statin non-adherence and discontinuation is statin-associated muscle symptoms (SAMS)⁴. SAMS, comprising a heterogeneous group of muscle symptoms including pain/aching, stiffness, tenderness or cramps, usually with normal or minimally elevated creatinine kinase levels, is prevalent challenge in clinical practice⁴. In contrast, serious statin side-effects, including liver failure, rhabdomyolysis, or myositis with elevated creatinine kinase levels in blood, are very rare^{4,5}. In randomized trials, statin therapy appears to cause only a slightly increased risk of side-effects of 1-5% compared with placebo, far below the prevalence reported in clinical practice, amounting to 30% in observational studies^{6,7}. Strict entry criteria in the randomized statin trials, excluding patients with polypharmacy, multiple comorbidities, elderly, females and low body weight, factors that predispose to musculoskeletal symptoms, may in part explain the diverging frequency of SAMS⁴. A major limitation of observational studies is a lack of blinding. Patients on statins may expect to experience side-effects, and therefore report a higher percentage than in a comparable population not on statins, the so-called 'nocebo' effect. Two previous studies, in subjects without cardiovascular disease, has tested whether SAMS reported by the patients are related the statin therapy⁸⁻⁹. In a randomized, double-blind crossover study that included patients complaining of SAMS at study start, only 36% experienced that their muscle symptoms persisted during treatment with simvastatin 20 mg and disappeared during placebo treatment⁸. Accordingly, SAMS was confirmed to be related to the statin treatment in one-third of the patients. The proportion of CHD patients with confirmed SAMS, treated with potent statins recommended for these patients, remains unknown. Furthermore, the clinical presentation (i.e. location, intensity and characteristics) of the muscle symptoms in CHD patients with and without confirmed SAMS remains to be investigated.

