1.2.2 Secondary Objectives

The secondary objectives of this study are:

- To determine the proportion of patients who report muscle symptoms on atorvastatin treatment compared with on placebo (dichotomous SAMS classification)
- To determine the correlation between muscular symptom intensity and blood concentrations of parent drug and metabolites of atorvastatin in patients with confirmed SAMS*
- To determine the diagnostic properties of blood concentrations of parent drug and metabolites of atorvastatin for classification of confirmed SAMS*
- To determine adherence to the study medication (i.e. atorvastatin and placebo) during the treatment periods
- To compare blood concentrations of parent drug and the metabolites of atorvastatin between patients with failing placebo-test (i.e. non-SAMS)* for connecting SAMS to atorvastatin and the control group without muscle symptoms
- To describe study safety

**Confirmed SAMS is defined as at least $\geq 25\%$ higher mean muscle symptom intensity (measured on a 0-10 cm Visual Analogue Scale [VAS]) and a 1cm difference during the last 3 weeks on treatment with atorvastatin compared to placebo. All other patients in the are defined as non-SAMS.*

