2.3 Sample size

Sample size calculations are based on our being able to detect a 1 cm difference in the VAS symptom score between the treatment periods on atorvastatin and placebo since the smallest change in VAS symptom score corresponding to ‘a little more’ or ‘a little less’ symptoms was 1.3 cm, with a lower limit of the CI at 1 cm in a previous study by Gallagher et al¹⁴. Gallagher et al. report a standard

STATISTICAL ANALYSIS PLAN for MUScle Side-Effects of atorvastatin in coronary patients (MUSE) – a randomized controlled trial

deviation (SD) of 1.7 for a difference of 1.0 between two VAS symptom scores. Because of the differences in both populations and specific VAS scale between that study in this one, we use SD=2.5 to account for a much larger variation in this study. With n=68, we will have 90% power to detect a difference of 1.0, using a one-sample T test. With n=68, we will also have 80% power to detect a difference of 40% SAMS under statins vs. 15% SAMS under placebo, using the McNemar test for paired probabilities. To account for some missing information due to drop-outs or and protocol deviations, we plan to include 80 patients.

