5.1 General Definitions and Derived Variables

5.1.1 Muscular symptom intensity

Individual mean difference in muscular symptom intensity = Mean muscular symptom intensity (regardless of characteristics and location) reported by the patient the last three weeks during the treatment period on atorvastatin – the last three weeks during the treatment period on placebo. The last consecutive three weeks completed during each treatment period will be used in patients who discontinue due to intolerable muscle symptoms.

Muscular symptom intensity is reported through a 0-10 cm Visual Analogue Scale (VAS) in a patient diary delivered at study start. The patients are asked to also report muscular symptom intensity on a 0-10 Likert scale. Results from the VAS scale will be replaced by the results from the Likert scale in case of missing data on the VAS scale.

VAS scores over the last 3 weeks in each treatment period have been chosen as primary end-point for three reasons: i) to ensure steady state concentrations of atorvastatin; ii) to maximize the likelihood for the symptoms reported to being truly related to the current (and not previous) treatment period; iii) the duration of the treatment period being sufficiently long to produce SAMS (>3 weeks). VAS score has also been chosen as primary outcome in two previous SAMS studies^{16,17}.

5.1.2 The proportion of patients who report muscle symptoms on atorvastatin treatment compared with on placebo (dichotomous SAMS classification)

The proportion of patients who report muscle symptoms on atorvastatin treatment and not on placebo (dichotomous SAMS classification). A 25% intra-individual change in the VAS symptom score has been regarded clinically relevant in a previous validation study of the scale¹⁴. As previously described it has been reported as the smallest change in VAS symptom score corresponding to ‘a little more’ or ‘a little less’ symptoms was 1.3 cm, with a lower limit of the CI at 1.0 cm in a previous study by Gallagher et al¹⁴. Accordingly, confirmed SAMS will be defined as a 25% higher individual VAS score during the treatment period on atorvastatin vs. placebo and ≥ 1.0 cm absolute difference.

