5.3 Secondary Outcomes Definitions

5.3.1 Dichotomous SAMS classification

The proportion of patients with confirmed SAMS, as defined in Section 5.1.2, where the mean of the symptoms scores in the last three weeks of each treatment period is used.

5.3.2 Relationship between muscle symptom intensity and atorvastatin and metabolites level in blood

The correlation between individual differences in mean muscular symptom intensity and atorvastatin and metabolites in blood plasma among patients with confirmed SAMS, as defined in Section 5.1.2. The 20 variables in Table 1 will be used.

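### SAP 2.3 claims 80% power for a McNemar comparison of SAMS on statin and on placebo, but Section 6 contains no such test and no defined outcome corresponds to the 15% on placebo

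*SAP*

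**What the plan says.** - **Power (2.3).** After the power statement for the primary outcome, the SAP adds that the same 68 patients give "80% power to detect a difference of 40% SAMS under statins vs. 15% SAMS under placebo, using the McNemar test for paired probabilities". It does not say whether the two percentages are marginal rates or discordant cells.
- **Objective (1.2.2).** The first secondary objective is "To determine the proportion of patients who report muscle symptoms on atorvastatin treatment compared with on placebo (dichotomous SAMS classification".
- **Definition (1.2.2 footnote, 5.1.2).** In 5.1.2, "confirmed SAMS will be defined as a 25% higher individual VAS score during the treatment period on atorvastatin vs. placebo", together with an absolute difference of at least 1.0 cm. The footnote in 1.2.2 then adds: "All other patients in the are defined as non-SAMS".
- **Outcome and analysis (5.3.1, 6.4.1).** The outcome is "The proportion of patients with confirmed SAMS, as defined in Section 5.1.2". It "will be estimated as the number of patients with confirmed SAMS divided by the total number of patients in the full analysis set", with a Wilson 95% interval and no test.
- **Status (2.4.1).** All efficacy analyses other than the primary one are supportive or exploratory.

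**The concern.** The power statement belongs to an analysis that the plan does not specify. A McNemar test needs two paired counts: either patients positive on one treatment only, in each direction, or a positive/negative status in each period. The SAP has neither. It defines one class in one direction and places everyone else, including a patient who is clearly worse on placebo, in the complement.

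This bears on interpretation. A count of patients whose atorvastatin mean exceeds their placebo mean by a threshold is above zero even with an inert drug, because period means vary within a patient. The Wilson interval describes sampling error of that count; it cannot separate a drug effect from this background. The placebo-worse count would be the natural reference, and it is lost in the merge. SAP 1.1 summarises an earlier crossover trial by one such proportion and concludes that "SAMS was confirmed to be related to the statin treatment in one-third of the patients", so a causal reading of a single proportion is a realistic risk here too.

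**Working it through.** **1. Reproduce the stated power.** Inputs: n = 68, 40% and 15% (2.3); two-sided alpha 0.05 (3.1). With discordant cells p10 and p01, s = p10 + p01 and d = p10 − p01:

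power = Φ[(d√n − 1.960√s) / √(s − d²)]

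Taking 40% and 15% as the discordant cells, s = 0.55 and d = 0.25:

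(0.25 × 8.246 − 1.960 × 0.7416) / √(0.55 − 0.0625) = (2.0616 − 1.4536) / 0.6982 = 0.871, so power = 80.8%.

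The same formula needs 66.7, that is 67, pairs for 80%. Enumerating the tests at n = 68 gives 81.6% (asymptotic), 81.2% (mid-P) and 76.9% (exact conditional).

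**2. Read the percentages as marginal rates instead.** If a fraction p11 is positive in both periods, p10 = 0.40 − p11 and p01 = 0.15 − p11. The SAP gives no p11, so it is varied as an assumption.

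| p11 | Power, normal approximation | Power, exact test |
|---|---|---|
| 0 | 80.8% | 76.9% |
| 0.04 | 87.0% | 83.6% |
| 0.06 (independence, 0.40 × 0.15) | 90.0% | 87.4% |
| 0.10 | 95.4% | 94.9% |

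The stated 80% therefore fits discordant cells, or margins with no patient positive in both periods. On the first reading the 15% is a placebo-worse class, which the SAP never defines.

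**3. Look for that class or test elsewhere.** Section 6 has no McNemar test. The nearest item is the −1/0/1 coding of symptom location in 5.3.7. It is not SAMS status, and 6.4.7 compares it between confirmed SAMS and non-SAMS patients, not between treatments.

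**4. Size of the one-direction proportion with an inert drug (illustration).** As a first look, take normal differences with mean zero and the 1 cm criterion alone: the proportion is 1 − Φ(1/SD).

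- SD 2.5 ("we use SD=2.5 to account for a much larger variation in this study"): 1 − Φ(0.400) = 34%
- SD 1.7 (the figure 2.3 cites from the VAS validation study): 1 − Φ(0.588) = 28%
- SD 1.0 (assumed): 1 − Φ(1.000) = 16%

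Adding the 25% criterion and bounding scores to 0–10 cm, simulation (300,000 patients per setting, mean levels 2–6 cm, between-patient SD 0.5–2) gives about 27–34%, 20–28% and 9–16% respectively. The symptom levels and between-patient SDs are assumptions.

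**5. What each analysis would report at n = 68.**

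- Inert drug, 20 patients classified (an example): 20/68 = 29%, Wilson 20% to 41%. The interval is well clear of zero with no drug effect.
- Planned cells, 27 and 10 patients: 6.4.1 would report 27/68 = 40%, Wilson 29% to 52%. The paired difference is (27 − 10)/68 = 25 points, Tango 95% CI 8 to 41. McNemar: 17²/37 = 7.81, P = 0.005.

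**The case against.** **The objective may already be met.** The footnote to 1.2.2 builds the placebo contrast into the classification, and 5.1.2 describes the outcome as symptoms on atorvastatin but not on placebo. On that reading 1.2.2, 5.1.2, 5.3.1 and 6.4.1 agree, and the outlier is one sentence in 2.3. This stands in part. A reader might infer that the comparison in 1.2.2 has no analysis behind it; the text does not support that. The objective is ambiguous: it can mean the within-patient classification that 6.4.1 reports, or the paired comparison that 2.3 powers. The mismatch with 2.3 remains on either reading.

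**Little depends on it.** The primary t-test alone supports n = 68: power for 1.0 cm with SD 2.5 recomputes to 90.2% against the stated 90%. The only decision rule is the primary one (2.4.2), and 6.3 already tests the same VAS difference on its full scale. All of this stands and limits the weight of the point.

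**A mirror class does not recover the share with true SAMS.** Correct. If every patient had a true 1 cm effect with SD 2.5, the 1 cm rule alone would put 50.0% in the confirmed class and 21.2% in the mirror class, a difference of about 29 points although all are affected. The paired difference tests asymmetry and should be described so.

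**The causal reading is a prediction.** The SAP attaches no inference to the Wilson interval, and 1.1 speaks of another study. That is fair; it is a risk of misreading, not a stated claim.

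**Conclusion.** The inconsistency is real and narrow. The SAP states power for a paired comparison that it neither defines nor performs, and the reported proportion lacks the placebo-worse count that would put it in context.

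Three stronger readings are not supported:

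- That the 80% is miscalculated: it reproduces at 80.8% for discordant cells.
- That 80% is a guaranteed minimum: the exact test on the cells gives 76.9%.
- That the trial's size or primary conclusion is in doubt: both rest on 6.3 and the t-test.

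The contradiction and the power figures are firm. The inert-drug rates of about 9–34% are not. They rest on assumed SDs and symptom levels, and since 2.5 was chosen deliberately large, the upper end may overstate them. They show that the background is not negligible, not how large it will be in this trial.

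**What to change.** Either of two changes resolves it.

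1. **Add the paired analysis.** In 5.1.2 and 5.3.1 define the mirror class: placebo mean at least 25% and at least 1.0 cm above the atorvastatin mean. In 6.4.1 report both proportions and their paired difference with a 95% CI (for example Tango or Newcombe) and an asymptotic or mid-P McNemar P-value. Describe the result as a test of asymmetry, not as the share of patients with true SAMS. The Wilson interval can stay as descriptive. In 2.3 state that 40% and 15% are discordant cells (about 81% power). If they were meant as marginal rates, define a per-period SAMS status, run the test on that status and state the assumed both-positive rate.
2. **Remove the claim.** Delete the McNemar power sentence from 2.3, reword the objective in 1.2.2 to estimating the proportion with confirmed SAMS, and note in 6.4.1 that this proportion is not zero with an inert drug.

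Cost: option 2 is wording only. Option 1 with discordant cells is wording and a few lines of code on diary data already collected; a per-period status would need a new definition. Under option 1 the paired difference is smaller than the raw proportion and its interval wider (in the planned-cells example, 25 points with an interval about 33 points wide, against 40% with one about 23 points wide).

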6.4.3 Diagnostic properties of atorvastatin and metabolites for classification of confirmed SAMS

Methods for analysis of ROC curves and measures of diagnostic accuracy will be used to identify cut-off values of metabolite concentrations that can discriminate between confirmed SAMS and non-SAMS. These methods include calculating sensitivity, specificity, and area under the ROC curve (with 95% confidence intervals).

STATISTICAL ANALYSIS PLAN for MUScle Side-Effects of atorvastatin in coronary patients (MUSE) – a randomized controlled trial

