Although several mechanisms have been proposed, it remains unclear how statins produce muscle symptoms, and reliable diagnostic biomarkers for the prediction or diagnosis of SAMS are lacking^{4,5}. For patient follow-up it is highly relevant to identify markers that predict the occurrence of muscle symptoms, and thus enable preventive actions. Individual variations in statin pharmacokinetics, mitochondrial dysfunction or coenzyme Q10 deficiency are suggested mechanisms for SAMS^{4,5}. A few observation studies indicate that pharmacokinetic alterations in statin metabolites may contribute to SAMS^{10,11}. The lactone metabolites of statins seem to be most potent in inducing myotoxic effects compared to the corresponding acid metabolites¹⁰. Accordingly, plasma concentrations of atorvastatin lactones have been associated with clinical muscle symptoms¹¹. In the present project we will determine the relationship between muscle symptoms and blood levels of atorvastatin metabolites using our liquid chromatography mass spectrometry method¹². Importantly, we have pilot data indicating significantly higher levels of atorvastatin lactone metabolites (sufficient for statistical significance) in patients reporting subjective SAMS, compared with those not reporting muscle symptoms¹³. If statin metabolite levels prove to be significantly stronger correlated with subjective muscle symptoms in patients with confirmed SAMS compared to those without in a randomized placebo-controlled study, this may pave the way for diagnostic testing of confirmed SAMS.

STATISTICAL ANALYSIS PLAN for MUscle Side-Effects of atorvastatin in coronary patients (MUSE) – a randomized controlled trial

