3.1 Confidence Intervals and P-values

All calculated P-values will be two-sided and compared to a 5% significance level. If a P-value is less than 0.05, the corresponding treatment difference will be denoted as statistically significant. All efficacy estimates will be presented with two-sided 95% confidence intervals. As there is only one primary null hypothesis to be tested in this trial, there will be no adjustments for multiplicity.

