5.3.3 Diagnostic properties of atorvastatin and metabolites for classification of confirmed SAMS

Sensitivity, specificity, and area under the ROC curve of blood concentrations of parent drug and the metabolites of atorvastatin for the classification of confirmed SAMS, as defined in Section 5.1.2. The 20 variables in Table 1 will be used.

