6.4.10 Pharmacogenetics

- (i) The mean value of the atorvastatin exposure variable with the highest area under the ROC curve (from the analyses in Section 6.4.3) will be compared between the different genotypes in the genetic variables SLCO1B1, CYP3A5, and CYP3A4 (see Section 5.3.11). The mean (standard deviation) for each genotype will be presented, with a P-value for a test of the null hypothesis of equal means. The two-sample T test with adjustment for unequal variances will be used for CYP3A5 and CYP3A4 (two genotypes) and ANOVA will be used for SLCO1B1 (three genotypes).
- (ii) The frequency of SLCO1B1, CYP3A4, and CYP3A5 genotypes will be compared among patients with confirmed SAMS (see definition in Section 5.1.2), non-SAMS and controls (see Figure 1, the study flow chart) with a Pearson chi-squared mid-P test for unordered r x c tables²¹. The comparisons for CYP3A4/5 will only be performed if there is a statistically significant difference between the genotypes in the atorvastatin exposure variable in (i).

STATISTICAL ANALYSIS PLAN for MUScle Side-Effects of atorvastatin in coronary patients (MUSE) – a randomized controlled trial

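### Sensitivity and specificity will be reported at cut-offs chosen in the same patients, across 20 variables and without optimism correction, so they will look better than they are

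*SAP*

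**What the plan says.** Determining the diagnostic properties of atorvastatin and its metabolites for confirmed SAMS is a named secondary objective (SAP section 1.2.2). Section 5.3.3 defines the outcome as sensitivity, specificity and area under the ROC curve, and adds: "The 20 variables in Table 1 will be used". Section 6.4.3 says that ROC methods will be used "to identify cut-off values of metabolite concentrations that can discriminate between confirmed SAMS and non-SAMS", with 95% confidence intervals.

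The SAP does not say how a cut-off is chosen or whether high or low concentrations count as positive. It names no split sample, cross-validation, bootstrap or external validation. Section 3.1 states that there is no multiplicity adjustment.

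Section 6.4.10 takes forward "the atorvastatin exposure variable with the highest area under the ROC curve" for comparison between genotypes, so the 20 variables are ranked by AUC. Section 5.1.3 marks in bold the Table 1 variables thought most likely to be related to SAMS, but sections 5.3.3 and 6.4.3 are not limited to them.

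**The concern.** A cut-off picked because it separates two groups well in one sample also fits the chance features of that sample. Sensitivity and specificity computed there describe the fit, not what the cut-off would achieve in new patients. Searching 20 variables adds a second layer of selection whenever one of them is put forward as best. An ordinary 95% interval around the selected result allows for neither step.

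Sensitivity and specificity at a stated cut-off are the figures that a reader would carry into a proposed diagnostic test. With a sample of this size, a marker of no value could be reported as having modest discriminating ability.

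**Working it through.** **Inputs from the SAP.** Section 2.3 says "With n=68, we will have 90% power to detect a difference of 1.0, using a one-sample T test" and "we plan to include 80 patients". The SD is 2.5 and the test is two-sided at 5%. The exact noncentral-t calculation with n = 68 gives 90.2%, so the stated 90% is reproduced. That figure only shows where 68 comes from; the SAP gives no figure for the ROC analysis. Table 1 has 20 variables, six of them sums of other listed variables (acids, lactones, and both together, at C0 and C2).

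**Assumptions the SAP does not supply.**
- Sample: 68 or 80 patients. Secondary analyses use the FAS (section 6.4), and section 3.3 removes partially adherent or non-adherent patients from blood-level analyses.
- Confirmed SAMS: 25%, 36% or 40%. The 36% is the earlier crossover result cited in section 1.1.
- Cut-off rule: maximum Youden index, J = sensitivity + specificity − 1.
- Correlation between markers: 0 to 0.8.

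**Closed-form check, no true association, 27 confirmed and 41 non-SAMS (40% of 68).**
- Cut-off optimism for one marker, direction fixed. The large-sample mean of the maximised J is √(π/8) × √(n/(n₁n₀)) = 0.627 × √(68/1107) = 0.155. The true value is 0.
- SD of one null AUC: √((n+1)/(12·n₁n₀)) = √(69/13284) = 0.072.
- Direction chosen from the data, one marker: mean AUC 0.5 + 0.072 × √(2/π) = 0.56.
- Highest AUC of 20: the expected maximum of 20 standard normals is 1.867. The mean is then about 0.5 + 1.867 × √(1−ρ) × 0.0721, treating the AUCs as correlated like the markers. This gives 0.635 for ρ = 0, 0.595 for ρ = 0.5 and 0.560 for ρ = 0.8.

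**Simulation, 1,500 null trials per scenario, cut-off chosen and evaluated in the same patients.**

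One marker, direction fixed: mean AUC is 0.50, so there is no bias. Sensitivity + specificity is 1.14 to 1.16 at n = 68 and 1.13 to 1.14 at n = 80. With direction read from the data, mean AUC is 0.56 to 0.57 at n = 68.

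Marker with the highest AUC of 20, direction fixed, 36% confirmed SAMS:

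| Correlation structure | n | Mean AUC | Sens + spec | Unadjusted 95% CI wholly above 0.5 |
|---|---|---|---|---|
| Equal, 0.8 | 68 | 0.56 | 1.22 | 12% |
| Equal, 0.5 | 68 | 0.60 | 1.26 | 25% |
| Table 1 with sums, 0.7 | 68 | 0.57 | 1.23 | 16% |
| Table 1 with sums, 0.3 | 68 | 0.61 | 1.27 | 27% |
| Equal, 0 (limit only) | 68 | 0.64 | 1.31 | 43% |
| Equal, 0.8 | 80 | 0.56 | 1.20 | 12% |
| Equal, 0.5 | 80 | 0.59 | 1.24 | 24% |

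The last column would be about 2.5% for one marker named in advance. Over 25% to 40% confirmed SAMS at n = 68, the sum runs from 1.21 to 1.34. The upper end needs zero correlation, which cannot hold when six variables are sums of others.

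**The case against.** A reader might infer that every AUC reported under section 6.4.3 is too high. The SAP does not support that. The AUC uses no cut-off, and 20 AUCs with directions set in advance are each unbiased. Section 6.4.3 does not say that only the best will be shown. Section 6.4.10 uses the highest AUC to choose an exposure variable for the genotype comparison; it does not present that AUC as diagnostic accuracy, and nothing calculated here shows bias in the genotype comparison.

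A reader might also lean on the remark in section 1.1 that "this may pave the way for diagnostic testing of confirmed SAMS". That sentence is conditional on a stronger correlation between metabolite levels and symptoms. It does not concern the ROC cut-offs, so it adds nothing to this point.

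The plan has some protection already. Section 2.4.1 calls all non-primary efficacy analyses supportive or exploratory, section 3.1 is open about multiplicity, and Table 1 flags the likely variables in advance. The list of methods in section 6.4.3 is also not exhaustive, so a correction is unspecified rather than excluded. All of this stands and limits the weight of the point. It does not remove the bias from sensitivity and specificity: an exploratory label does not change an estimate, and the flagged variables are not given priority in the ROC analysis.

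**Conclusion.** The point holds for sensitivity and specificity at data-chosen cut-offs. Under the stated assumptions, the excess in their sum is about 0.15 for one uninformative marker and about 0.2 to 0.3 for the best of 20. The lower part of that range is more plausible because these are one drug and its metabolites, with sums included. Moving from 68 to 80 patients reduces the excess only slightly.

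For the AUC the point is conditional. It applies to a marker presented as best (null mean about 0.56 to 0.60 at correlations of 0.8 to 0.5), or where direction is read from the data (about 0.56 to 0.57 for one marker). The sizes rest on the Youden rule, the sample size, the SAMS share and the correlations, none of which the SAP fixes for this analysis. The existence of optimism does not depend on their exact values: it appeared in every scenario tried. This is a worthwhile improvement to a secondary analysis.

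**What to change.** Amend section 6.4.3 to:
- state the cut-off rule and, for each variable, the direction that counts as positive;
- make the Table 1 variables already in bold the lead markers, and call the others exploratory;
- report bootstrap optimism-corrected sensitivity and specificity beside the apparent values, repeating the cut-off choice in each resample, and the marker choice too for any statement about a best marker;
- correct the AUC only for a marker presented as best;
- label the cut-offs as needing external validation.

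The cost is SAP wording, a few hours of programming, and slightly less favourable accuracy figures. No new data or design change is needed.
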